9.2.2. Reporting Serious Adverse Events

The Sponsor(s) will collect SAEs from the signing of the Informed Consent Form. If the patient is definitively included in the study, this information will also be recorded in the AE section of the CRF.

SAEs will be collected until 30 days after administration of the last dose of study drug/IMP or until the start of a new antitumor therapy, whichever occurs first. Beyond this period of time, only those SAEs suspected to be related to the IMP/s need to be reported. Nonetheless, the Sponsor(s) will evaluate any safety information that is spontaneously reported by an Investigator beyond the time frame specified in the protocol.

All SAEs (as defined above) regardless of relationship to the study drug/IMP must be reported immediately and always within 24 hours to the PharmaMar Pharmacovigilance function by fax ([contact]) or telephone ([contact]). Out of office hours (GMT), assistance on SAE reporting can be obtained by calling the Pharmacovigilance Service at [contact].

The preferred reporting method is by faxing the completed SAE form. An initial report by telephone must be followed by a completed “Serious Adverse Event Form” from the investigational staff within one working day.

All SAEs suspected to be related to the IMP/s must be followed until the event or its sequelae resolves or stabilizes at an acceptable level by the Investigator and the clinical monitor or his/her designated representative.

Exemptions from SAE REPORTING: Events of “disease progression” even if they fulfill any seriousness criterion (i.e. fatal, requiring hospitalization, etc) are exempted from SAE reporting and will only be reported in the applicable CRF page.

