9. ADVERSE EVENTS REPORTING

9.1. DEFINITIONS

9.1.1. Adverse Event

An adverse event (AE) is any untoward medical occurrence in a patient or a clinical investigation patient administered a pharmaceutical product which does not necessarily have a causal relationship with this treatment.

An AE can therefore be any unfavorable and unintended sign (e.g., an abnormal laboratory finding), or a disease temporally associated with the use of a medicinal product, whether or not considered related to the medicinal product.

Any event involving adverse drug reactions, illnesses with onset during the study or exacerbations of pre-existing illnesses should be recorded, including but not limited to clinically significant changes in physical examination findings and abnormal objective test findings (e.g., ECG). The criteria for determining whether an abnormal objective test finding should be reported as an AE are as follows:

- The test result is associated with clinically significant symptoms, and/or,
- The test result leads to a change in the study dosing or discontinuation from the clinical trial, significant additional concomitant drug treatment or other therapy, and/or,
- The test result leads to any of the outcomes included in the definition of a SAE and/or,
- The test result is considered to be an AE by the Investigator.

Tumor progression or appearance of new tumor lesions MUST NOT be reported as an AE.

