9.1.2. Serious Adverse Event

A Serious Adverse Event (SAE) is any adverse experience occurring at any dose that:

- Results in death (is fatal),
- Is life-threatening,
- Requires or prolongs inpatient hospitalization,
- Results in persistent or significant disability or incapacity,
- Is a congenital anomaly or birth defect,
- Is medically significant, or
- Is any suspected transmission of an infectious agent via a medicinal product.

Medical and scientific judgment should be exercised in deciding whether expedited reporting is appropriate in other situations such an important medical event that may not be immediately life-threatening or result in hospitalization but may jeopardize the patient or may require intervention to prevent one of the outcomes listed in the above definition.

Tumor progression or appearance of new tumor lesions MUST NOT be reported as a SAE.

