9.1.2.3. Hospitalization or Prolongation of Hospitalization

Any AE requiring hospitalization (or prolongation of hospitalization) that occurs or worsens during the course of a patient's participation in a clinical trial must be reported as a SAE unless exempted from SAE reporting (see Section [9.2.2](#)). Prolongation of hospitalization is defined as any extension of an inpatient hospitalization beyond the stay anticipated/required for the initial admission, as determined by the Investigator or by the treating physician.

Hospitalizations that do not meet criteria for SAE reporting are:

- a. Reasons described in protocol [e.g., investigational medicinal product (IMP) administration, protocol-required intervention/investigations, etc]. However, events requiring hospitalizations or prolongation of hospitalization as a result of a complication of therapy administration or clinical trial procedures will be reported as SAEs.
- b. Hospitalization or prolonged hospitalization for technical, practical or social reasons, in absence of an AE.
- c. Pre-planned hospitalizations: any pre-planned surgery or procedure must be documented in the source documentation. Only if the pre-planned surgery needs to be performed earlier due to a worsening of the condition, should this event (worsened condition) be reported as a SAE.

Other situations that MUST NOT be considered as hospitalizations are the following:

- d. An emergency visit due to an accident where the patient is treated and discharged.
- e. When the patient is held 24 hours for observation and finally is not admitted.
- f. Planned treatments at sites not associated to a hospital and generally considered as minor surgical procedures (e.g., laser eye surgery, arthroscopy, etc).

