9.1.4. Assessment of Causal Relationship to the Study Drug/IMP

The Investigator must provide an assessment of causal relationship of the clinical trial IMPs to each SAE according to the following scale:

- Y** There is a reasonable possibility that the IMP caused the SAE.
- N** There is no reasonable possibility that the IMP caused the SAE and other causes are more probable.
- Uk.** Only to be used in special situations where the Investigator has insufficient information (i.e., the patient was not seen at his/her centre) if none of the above can be used.

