9.1.5. Adverse Events Related to Study Drug (IMP)

An AE is considered related to a study drug/IMP if the Investigator's assessment of causal relationship to the IMP is "Y" (yes).

The Investigator will assess the causal relationship of each of the IMP to the SAE.

The Sponsor(s) will also consider related to the study drug/IMP those events for which the Investigator assesses the causal relationship with the IMP as "Uk" when it cannot rule out a role of the IMP in the event. See Section [9.1.4](#) for causality scale.

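### The progression exemption from AE and SAE reporting has no exception for a serious event in which the investigator also suspects Zalypsis

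*Protocol*

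**What the plan says.** Four places in the protocol take progression out of safety reporting.

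- Section 9.1.1 (AE definition): "Tumor progression or appearance of new tumor lesions MUST NOT be reported as an AE".
- Section 9.1.2 (SAE definition): "Tumor progression or appearance of new tumor lesions MUST NOT be reported as a SAE".
- Section 9.2.1 (AE procedure) says that progression is not an adverse event and goes on its own CRF page.
- Section 9.2.2 (SAE procedure): "Events of “disease progression” even if they fulfill any seriousness criterion (i.e. fatal, requiring hospitalization, etc) are exempted from SAE reporting". Such events again go to the CRF page only.

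The safeguards that might catch a drug contribution depend on SAE status. Section 9.1.2.3 says that an adverse event requiring hospitalization "must be reported as a SAE unless exempted from SAE reporting". Section 9.1.4 says: "The Investigator must provide an assessment of causal relationship of the clinical trial IMPs to each SAE". The 24-hour report in Section 9.2.2 is for SAEs as the protocol defines them, and the sponsor's duty in Section 9.1.6 to inform investigators and ethics committees is for SAEs that are unlisted and related. SAP Section 12.2.3 takes the study report's SAE listings from the Pharmacovigilance department.

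Two sentences point the other way. Section 9.1.1 asks for events involving adverse drug reactions to be recorded. Section 9.1.2 leaves room for medical judgment on expedited reporting in situations outside its list.

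**The concern.** Exempting progression from SAE reporting is ordinary in an oncology trial, and an event that the investigator reads as progression alone is rightly exempt. The difficulty is the event with two suspected causes. A patient is admitted with worsening pain, bleeding or organ dysfunction, and the investigator thinks that the tumor is growing but also that the drug may have contributed. The exemption makes no allowance for that suspicion.

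Such an event is plausible here. Every patient enters with documented progression, and scans come only every other cycle, so between scans the label has to be clinical. Section 9 gives no criterion for using it. At the same dose and schedule in phase I, tumor flare and tumor pain were among the drug-related SAEs (Section 1.2.5.1.1), and both can look like progression.

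At stake is the speed and completeness of safety information on a drug without a data safety monitoring board (Section 9.2.4). No efficacy conclusion depends on it.

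**Working it through.** This is a check of rules against each other. The only arithmetic concerns the phase I context.

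**Step 1: look for a condition on the exemption.** The AE, SAE, causality, death and expedited-reporting sections of the protocol and the safety sections of the SAP were read for any wording that limits the exemption to events not suspected to be drug-related. There is none.

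**Step 2: follow a non-fatal hospitalization that the investigator labels progression while also suspecting Zalypsis.**

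| Safeguard | Applies to | Reaches the event? |
|---|---|---|
| Hospitalization rule, 9.1.2.3 | AEs not exempted | No, it defers to the exemption |
| Causality scale, 9.1.4 | Each SAE | No |
| 24-hour report, 9.2.2 | SAEs as defined | No; it covers SAEs whatever their relationship to the drug, but this event is not an SAE |
| Notice to investigators and ethics committees, 9.1.6 | Unlisted, related SAEs | No |
| Study-report SAE listings, SAP 12.2.3 | What Pharmacovigilance holds | No, if nothing was sent there |
| Recording of drug reactions, 9.1.1 | Events involving a drug reaction | Arguably, but not ranked above the ban in the same section |
| Judgment on expedited reporting, 9.1.2 | Other situations | Arguably, but not ranked above the ban that follows it |
| Critical safety findings and ongoing oncologist review, 9.2.4 | Sponsor level | Possibly, once the sponsor learns of the event |

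Section 9.2.4 places the sponsor's safety review after CRFs have been monitored, collected and shipped. For an event recorded only on a CRF page, that does not replace a 24-hour report.

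**Step 3: the same event, fatal.** SAP Section 7.4.4 and Table 12.2.3.2 list deaths with a relationship column. Attribution can surface there, although only in an analysis listing. This is why the gap is mainly non-fatal.

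**Step 4: the main-diagnosis rule.** Section 9.2.1 prefers the main diagnosis to its signs and symptoms where possible. It does not tell the investigator to drop pain when progression coexists, and it does not say to keep it as a separate term.

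**Step 5: phase I context.** Section 1.2.5.1.1 reports 6 drug-related SAEs in 5 of 24 patients at 2 mg/m². Two occurred in one patient (nausea, neutropenic infection) and four in one patient each (diarrhea, tumor flare, tumor pain, pyrexia): 2 + 4 = 6 events and 1 + 4 = 5 patients. Flare or tumor pain: 2/24 = 8.3%, exact (Clopper-Pearson) 95% CI 1.0% to 27.0%. The tumor types in Section 1.2.5.1 sum to 29 + 7 + 5 + 8 = 49 patients, and none is listed as an Ewing tumor.

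**The case against.** The strongest reply is that the exemption names a diagnosis and does not cover everything that happens to a progressing patient. An investigator who suspects the drug has a second, non-exempt event to report, such as flare, pain, bleeding or organ toxicity. The recording duty in Section 9.1.1 and the discretion in Section 9.1.2 support that reading. Much of this stands: flare or tumor pain recognised as such is already reportable. It does not close the gap, because the bans are capitalised, the exemption is explicit, and the two helpful sentences are not said to override them. The rules conflict without a ranking.

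Section 9.1.2.3 also says that hospitalizations caused by complications of therapy are reported as SAEs. That sentence qualifies admissions planned in the protocol. It shows the intended spirit but does not address progression.

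A reader might infer that a dual-suspicion event can never reach the sponsor or regulators. The documents do not support that. Progression reaches the sponsor on its CRF page, a medical oncologist reviews safety data on an ongoing basis, and Section 9.2.4 commits the sponsor to expedited reporting of critical safety findings, a category separate from adverse events.

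A reader might also take 8.3% as the share of events that would be lost. It is not. Both phase I cases were recognised and reported as drug-related, so they lie outside the gap. They show only that tumor events can be attributed to this drug. The phase I reporting rules are not in these documents, and no misfiled case is shown.

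**Conclusion.** The concern holds in a narrow form. On the text, a serious event filed as progression in which the investigator also suspects Zalypsis can go only to a CRF page, and nothing states that the suspicion prevails. The consequence is a possible loss or delay of drug-related safety information, mainly for non-fatal events, with the partial backstops described above.

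Its size cannot be estimated: the documents do not say how often both causes are suspected or how such events are filed. The conclusion assumes only that some investigators will follow the exemption as written. The response rate, the first-stage stopping rule and the error rates do not depend on it. It merits consideration as a cheap improvement and nothing stronger.

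**What to change.** In Section 9.2.2, and mirrored in 9.1.1, 9.1.2 and 9.2.1, add that the exemption does not apply when the investigator suspects a causal relationship to Zalypsis. The clinical event (for example tumor flare, tumor pain, bleeding or organ dysfunction) is then reported under its own term as an AE or SAE, with a causality assessment, and within 24 hours if serious. Progression itself stays on its CRF page as an efficacy outcome and is not coded as an adverse event. In Section 9.2.1, state that the main-diagnosis rule does not absorb such an event into progression.

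The protocol already uses suspicion as a trigger: after the 30-day window, "only those SAEs suspected to be related to the IMP/s need to be reported". Make the trigger the investigator's suspicion, without waiting for RECIST documentation.

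Do not use the Uk category alone as the trigger. Section 9.1.4 describes it as "Only to be used in special situations where the Investigator has insufficient information", and under Section 9.1.5 the sponsor treats such an event as related "when it cannot rule out a role of the IMP in the event". The footnote to SAP Table 12.2.1.1 groups unknown with drug-related. Ordinary progression events managed at another hospital could then enter the drug-related rate.

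The cost is a short protocol amendment with ethics committee approval, a few more SAE forms and possibly a slightly higher drug-related SAE rate. No new visits, scans, tests, CRF fields or SAP tables are needed.

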9.2.3. Reporting Pregnancy Cases Occurring During the Clinical Trial

National regulations require that clinical trial Sponsor(s) collect information on pregnancies occurring during clinical trials, in which exposure to the IMPs at any time during pregnancy, via either maternal or paternal exposure, is suspected.

Therefore, pregnancy and suspected pregnancy (including a positive pregnancy test regardless of age or disease state) of a female patient or the female partner of a male patient occurring while the patient is on study drug, or within 30 days of the patient’s discontinuation visit, are considered immediately reportable events.

The Investigator will report the following events immediately and always within 24 hours from first knowledge:

- Any occurrence of a pregnancy where any kind of exposure to the IMP/s is suspected.
- Possible exposure of a pregnant woman (this could involve a partner of a male patient or a pregnant female who came in contact with the clinical trial IMP/s).

- All reports of elevated/ questionable or indeterminate beta human chorionic gonadotrophins (βhCGs).

Immediately after detecting a case of suspected pregnancy in a female clinical trial patient, the decision on her continued participation in the clinical trial will be jointly taken by the trial patient, the Investigator and the Sponsor(s), with the patient's best interest in mind. A decision to continue the pregnancy will require immediate withdrawal from the trial.

Any pregnancy, suspected pregnancy, or positive pregnancy test must be reported to PharmaMar Pharmacovigilance immediately by facsimile using the Pregnancy Report form. In the case of pregnancy of the female partner of a trial Patient the Investigator will obtain her informed consent to provide the information by using the applicable form provided by the Sponsor(s) who will also advise the Investigator in these situations.

The Investigator will follow the pregnancy until its outcome, and must notify PharmaMar Pharmacovigilance the outcome of the pregnancy within 24 hours of first knowledge as a follow-up to the initial report.

For any event during the pregnancy, which meets a seriousness criterion (including fetal or neonatal death or congenital anomaly), the Investigator will also follow the procedures for reporting SAEs (complete and send the SAE form to PharmaMar Pharmacovigilance by facsimile within 24 hours of the Investigator's knowledge of the event).

All neonatal deaths that occur within 30 days of birth should be reported, without regard to causality, as SAEs. In addition, any infant death at any time thereafter that the Investigator suspects is related to the exposure to the study drug/IMP should also be reported to PharmaMar Pharmacovigilance by facsimile within 24 hours of the Investigators' knowledge of the event.

9.2.4. Periodic Safety Review of Clinical Data

Although periodic safety review of clinical data will be performed, no formal Data Safety and Monitoring Board (DSMB) has been appointed for this exploratory, small sample-size trial. Adverse events will be monitored by the Investigators and by the study team at PharmaMar.

The personnel in charge of this process are defined on the section "Study Contacts" of the protocol. A medical oncologist will review the safety data of this trial on an ongoing basis.

SAEs will be collected, assessed and reported as per the applicable Regulations by the Pharmacovigilance Department / Regulatory Affairs Department.

In the case of an accumulation of unexpected SAEs, stopping guidelines have been established in the protocol (see Section 5.2).

As per the applicable regulations, the Sponsor(s) will report to IECs/IRBs, investigators and Regulatory Authorities:

- expeditely: all serious, related, unexpected AEs or critical safety findings from this and any other clinical trial with the same study drug/ IMP, and
- periodically: within an Annual Report: all the relevant safety information generated in all clinical trials with the study drug/ IMP.

Non-serious AEs will be assessed during monitoring visits by the monitor who will discuss them with investigators. Any protocol deviation will also be discussed with the investigator during monitoring visits. Safety review will be performed at PharmaMar once CRFs have been monitored, collected and shipped to the Sponsor(s).

10. STATISTICAL METHODS

The statistical analysis will be done by the Sponsor(s) or under the Sponsor(s)'s authority.

10.1. SAMPLE SIZE

The optimum two-stage design to test the null hypothesis that the overall response rate (ORR) is $\leq 3\%$ versus the alternative that $ORR \geq 20\%$ was selected. After testing the drug on 12 patients in the first stage, the trial will be terminated if there is not any responder. If the trial goes on to the second stage, a total of 29 patients will be studied, 12 from the first stage and 17 from the second stage. If the total number responding is less than or equal to 2 (two patients), the drug will be considered not interesting in the setting of patients treated with this disease and with this schedule. This design has an expected sample size of 17.20 and a probability of early termination of 0.69. If the drug is actually not effective, there is a 0.05 probability of concluding that it is (type I error). If the drug is actually effective, there is a 0.1 probability of concluding that it is not (type II error).

10.2. ENDPOINTS

10.2.1. Primary Endpoints

- Overall response rate (ORR), defined as the percentage of patients with confirmed O), either CR or PR, according to the RECIST v1.1.

10.2.2. Secondary Endpoints

Efficacy:

- Duration of response (DOR), defined as the time between the date when the response criteria (PR or CR, whichever is first reached) are fulfilled and the first date when disease progression, recurrence or death is objectively documented (taking the smallest measurements documented since the treatment started as reference for PD).
- Progression-free survival (PFS), defined as the time from the first day of study treatment to the day of negative assessment (progression or death), start of subsequent antitumor therapy, or last tumor evaluation. PFS at 3 and PFS at 6 months are defined as the Kaplan-Meier estimates of PFS at these time points.
- Overall survival (OS), defined as the time from the first day of treatment to the date of death (or the last day when the patient is known to be alive). Survival will be followed for up to six months after the last treatment visit of the last patient or 12 months after the last patient is included, whichever occurs first. OS at 12 months is defined as the Kaplan-Meier estimates of OS at this time point.

Safety:

- Clinical examinations.
- Vital signs analysis.

- Clinical assessment of AEs and SAEs.
- Changes in laboratory parameters: hematological and biochemical (including liver and cardiac function tests).
- Reasons for study discontinuations, dose delays, omissions, and reductions.
- Any other analyses that may be considered necessary to characterize the safety profile of Zalypsis® in patients with advanced and/or metastatic EFT.

Others:

- Pharmacokinetic profile.
- Pharmacogenomic profile.
- Pharmacodynamic profile.

10.3. STATISTICAL ANALYSIS

Continuous variables will be tabulated and presented with summary statistics (i.e., mean, standard deviation, median and range). Categorical variables will be summarized in frequency tables by means of counts and percentages.

10.3.1. Efficacy Analysis

All patients who have received at least four of the six infusions in the first two cycles (i.e., two infusions in each cycle, or three infusions in Cycle 1 and one infusion in Cycle 2), and at least one disease measurement recorded not less than six weeks after treatment onset.

In addition, any eligible patient who receives at least two of the three infusions in one treatment cycle and experience disease progression or die due to progressive disease (PD) prior to response evaluation will be considered evaluable for the main endpoint (ORR) and will be categorized as an “early progression”.

Patients withdrawn due to toxicity without any tumor assessment after the start of study treatment will be considered as “treatment failures” and will not be replaced.

Patients withdrawn due to significant clinical deterioration of unknown reason, hypersensitivity reactions, who refuse to continue on study for any reason or unrelated AEs without any tumor assessment after the start of study treatment, will be considered not evaluable for efficacy and will have to be replaced.

Assessment of efficacy will be done using the RECIST v. 1.1 and will be essentially based on a set of measurable lesions identified at baseline as target lesions and followed until disease progression. A disease evaluation will be performed at baseline and every other cycle (\pm 1 week) until evidence of PD. The same procedure will be used to evaluate each identified lesion both at baseline and throughout the treatment period.

In case of detection of an OR, either CR or PR, a confirmation assessment has to be performed a minimum of four weeks after the first documentation of the response.

Binomial estimates with exact 95% confidence intervals will be calculated for the analysis of the main endpoint (ORR).

Time-to-event endpoints (DOR, PFS and OS, PFS at 3 and 6 months and OS rates at 12 months) will be analyzed according to the Kaplan-Meier method.

